### After Week 4:

Subjects classified as clear at any of the on-treatment visits may stop the treatment at the investigator's discretion. They should remain in the trial and attend all visits up to and including the follow-up visit. The IPs will continue to be dispensed to the subject, and treatment may be restarted at the subject's discretion. The subject should not discontinue treatment themselves between visits, but is only allowed to stop using the treatment on the advice of the investigator at a scheduled visit.

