### 7.9.2 HPA axis suppression/ ACTH challenge test

For subjects assigned to the MC2-01 cream, adrenal function will be assessed in a challenge test with an intravenous dose of adrenocorticotropic hormone (ACTH) (cosyntropin). Measurement of serum cortisol levels pre- and post- stimulation with cosyntropin 0.25 mg is the accepted standard method used to evaluate adrenal suppression. The ACTH challenge test will be performed at Visit 1/Day 0, Week 4 and Week 8 visits. The test consists of blood sampling starting at 8 am ( $\pm$  30 minutes). Following the blood sample, an intravenous bolus injection of 0.25 mg cosyntropin is given at time zero (t=0 minutes). Serum cortisol concentration at t=30 minutes will reflect

stimulation of the adrenal glands induced by cosyntropin. The ACTH challenge test must be performed before application of the IP.

Since many people do not respond to the degree expected with cosyntropin stimulation, the following criteria have been established to denote a normal response:

1. pre-stimulation cortisol levels  $>5 \mu\text{g/dL}$  will be considered normal,
2. the 30-minute post-stimulation level should show an increment of  $\geq 7 \mu\text{g/dL}$  above the basal level, and
3. the 30-minute post-stimulation level should exceed  $18 \mu\text{g/dL}$ .

Therefore, a basal serum cortisol level  $\leq 5 \mu\text{g/dL}$ , or a 30-minute post-stimulation level  $\leq 18 \mu\text{g/dL}$ , or a post-stimulation increase (over basal)  $< 7 \mu\text{g/dL}$  constitutes the definition of HPA axis suppression in the trial.

Visit 1/Day 0: If HPA axis is suppressed at Visit 1/Day 0, the subject should be contacted because the application with the investigational product (IP) should be discontinued and an Early Termination visit should be performed (see [Section 7.16](#)).

Week 4: If HPA axis is suppressed at Week 4, the subject should be contacted and the application with the MC2-01 cream should be discontinued. The subject should continue in the trial and the ACTH challenge test is repeated at the Week 8 visit. If HPA axis suppression is noted at Week 8, the subject must return for a follow-up visit (see [Section 7.15](#)).

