### 7.13.6 Trial medication overdose

An overdose of the investigational product, i.e., a dose that is higher than the highest dose under clinical investigation or the known therapeutic dose, will be fully documented even if no toxic effects were observed and will be considered an AE.

The maximum weekly dose of the MC2-01 cream and the comparator is 100 g. The treated area should not be >30% of the body surface area.

Use above the recommended dose may cause elevated serum calcium, which should rapidly subside when treatment is discontinued. Excessive prolonged use of topical corticosteroids may suppress the pituitary-adrenal functions, resulting in secondary adrenal insufficiency that is usually reversible. In such cases, symptomatic treatment is indicated.

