## 9. DATA CONVENTIONS FOR ANALYSIS

### 9.1 General Statistical Principles

All statistical processing will be performed using the SAS system (Version 9.3 or higher).

All observed and derived variables (e.g., change from baseline) used in the summaries of analyses will be presented in by-subject listings. Descriptive statistics will be used to provide an overview of the safety and PK results. For categorical parameters, the number and percentage of subjects in each category will be presented. The denominator for percentage will be based on the number of subjects appropriate for the purpose of analysis. For continuous parameters, descriptive statistics will include number of observations, mean, standard deviation (SD), median, and range. The PK parameters will be summarised using appropriate descriptive statistics including median, lower and upper quartiles, minimum and maximum. Geometric means and coefficient of variation (CV) will be provided as appropriate.

It is planned that the data from all centers that participate in this protocol will be combined so that an adequate number of subjects will be available for analysis.

No interim analyses are planned.

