#### **10.8.2.2 Calcium Metabolism Endpoints**

All calcium metabolism data will be presented in a by-subject listing for the following parameters:

- Albumin-corrected serum calcium
- 24 hours urinary calcium excretion
- Ratio of urinary calcium to creatinine

Observed values and changes from baseline to Week 4 and Week 8 will be summarized using descriptive statistics for subjects in the Safety population assigned to MC2-01 cream.

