Generated on XXXXXX by XXXX / Uses: XXXX / Reference: Data Listing XXXX

Table 14.2.4.1 Summary of HPA-Axis Suppression (Based on Cosyntropin US Packing Insert)  
HPA Population

	MC2-01 Cream (N=XX)
HPA-Axis Suppression, n / N (%)	
Visit 3/ Week 4	XX/XX (XX.X)
Visit 5/ Week 8	XX/XX (XX.X)
HPA-Axis Suppressed at Week 4	XX/XX (XX.X)
HPA-Axis Not Suppressed at Week 4	XX/XX (XX.X)

Note: HPA-axis suppression is defined as a 30-minute post-stimulation cortisol level <18 µg/dL  
Generated on XX/XX/XX:XXXX by XXXXX / Uses: XXXX / Reference: Data Listings XXXX

*[Programming note: Denominator for Visit 5/Week 8 (Week 4 HPA-Axis Suppressed) row is subjects with HPA-Axis Suppressed at Week 8; denominator for Visit 5/Week 8 (Week 4 HPA-Axis Not Suppressed) row is subjects with HPA-Axis Suppressed at Week 8]*

Table 14.2.4.2 Summary of HPA-Axis Suppression (Based on Lab Reference Range)  
MC2-01 Cream Subjects with Baseline Cortisol Level  $\geq$  14  $\mu$ g/dl

MC2-01 Cream (N=XX)	
HPA-Axis Suppression, n / N (%)	
Visit 3/ Week 4	XX/XX (XX.X)
Visit 5/ Week 8	XX/XX (XX.X)
HPA-Axis Suppressed at Week 4	XX/XX (XX.X)
HPA-Axis Not Suppressed at Week 4	XX/XX (XX.X)

Note: HPA-axis suppression is defined as a 30-minute post-stimulation cortisol level  $<14 \mu$ g/dL  
Generated on XX/XX/XX:XXXX by XXXXX / Uses: XXXX / Reference: Data Listings XXXX

*[Programming note: Denominator for Visit 5/Week 8 (Week 4 HPA-Axis Suppressed) row is subjects with HPA-Axis Suppressed at Week 8; denominator for Visit 5/Week 8 (Week 4 HPA-Axis Not Suppressed) row is subjects with HPA-Axis Suppressed at Week 8]*

MC2 Therapeutics  
Protocol Number: MC2-01-C3

Page X of Y

Table 14.2.5 Summary of Calcium Metabolism  
HPA Population

MC2-01 Cream (N=XX)		
	Observed Value	Change from Baseline
Albumin-Corrected Serum Calcium (unit)		
Baseline		
N	XX	--
Mean (SD)	XX.X (XX.X)	--
Median	XX.X	--
Q1, Q3	XX, XX	--
Minimum, Maximum	XX, XX	--
Visit 3/Week 4		
N	XX	XX
Mean (SD)	XX.X (XX.X)	XX.X (XX.X)
Median	XX.X	XX.X
Q1, Q3	XX, XX	XX, XX
Minimum, Maximum	XX, XX	XX, XX
Visit 5/Week 8		
N	XX	XX
Mean (SD)	XX.X (XX.X)	XX.X (XX.X)
Median	XX.X	XX.X
Q1, Q3	XX, XX	XX, XX
Minimum, Maximum	XX, XX	XX, XX

<Continue for: 24 Hours Urinary Calcium Excretion (unit) and Ratio of Urinary Calcium to Creatinine>

MC2 Therapeutics  
Protocol Number: MC2-01-C3

Page X of Y

Table 14.2.6: Summary of Physician's Global Assessment (PGA)  
Safety Population

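### The Week 8 calcium summary pools subjects still applying cream with subjects who have stopped it, and no row shows the result under continued use

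*SAP*

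**What the plan says.** **The summary.** For albumin-corrected serum calcium, 24-hour urinary calcium and the urinary calcium:creatinine ratio, SAP 10.8.2.2 states that "changes from baseline to Week 4 and Week 8 will be summarized using descriptive statistics for subjects in the Safety population" assigned to cream. SAP 9.1 sets the content: "For continuous parameters, descriptive statistics will include number of observations, mean, standard deviation (SD), median, and range". The shell headed "Table 14.2.5 Summary of Calcium Metabolism" adds quartiles. It has one cream column and one Week 8 block per parameter, with no division by whether cream was still in use. The shell and the list of tables name the HPA population, while the text names the Safety population.

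**Two routes off cream before Week 8.**
- Protocol 7.9.2: "If HPA axis is suppressed at Week 4, the subject should be contacted and the application with the MC2-01 cream should be discontinued". It then adds: "The subject should continue in the trial and the ACTH challenge test is repeated at the Week 8 visit".
- Protocol 6.4, after Week 4: "Subjects classified as clear at any of the on-treatment visits may stop the treatment at the investigator's discretion". These subjects stay in the trial for their remaining visits and may restart at their own discretion.

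Protocol Table 7-2 and Section 7.9.4 schedule the Week 8 laboratory tests and urine collection by assigned arm, not by current use.

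**The contrast with HPA.** SAP 10.8.2.1 notes that subjects suppressed at Week 4 were told to stop the cream, and it splits the Week 8 HPA result by Week 4 status. SAP 10.8.1 lists calcium beside HPA as a primary safety endpoint, but calcium gets no comparable split.

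**Reversibility.** Protocol 7.13.6, on overdose, says that use above the recommended dose may cause "elevated serum calcium, which should rapidly subside when treatment is discontinued".

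**The concern.** The secondary objective concerns calcium metabolism under once-daily, maximum-use application. Protocol 2.2 says the cream is intended for daily use for up to 8 weeks, so Week 8 is where this trial looks at calcium after the full intended duration. The comparator arm ends at Week 4 and leaves no concurrent control at Week 8. The natural reading of Table 14.2.5 is therefore a comparison of Week 4 with Week 8 within the cream arm.

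The mixing bears directly on that comparison. At Week 4 every cream subject is meant to be on treatment, because Protocol 6.4 asks even subjects who are clear at Week 2 to continue unless the investigator finds further treatment unacceptable. At Week 8 an unknown share is not on treatment. If calcium drifts back towards baseline once cream stops, the Week 8 mean shrinks for a reason unrelated to how continued use affects calcium. A reader could then take a steady effect for a fading one.

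**Working it through.** The documents state no effect size, SD, stop rate or power for calcium, so there is no planned figure to reproduce. The check is a weighted mean under stated assumptions.

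**Inputs**
- n = 25: the Week 4 PK target per arm (Protocol 8.2), used only as a convenient denominator. About 60 subjects are to be enrolled 1:1, so the Safety set could be nearer 30 per arm.
- f = s/25: share off cream at Week 8 (assumed).
- g: true growth of the mean effect from Week 4 to Week 8 in those who continue (assumed).
- ρ: share of the effect left in those off cream (assumed).
- k: Week 4 effect of later stoppers relative to the others (assumed).

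**Formula**

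R = apparent Week 8 mean / Week 4 mean = [(1−f)(1+g) + f·k·ρ] / [(1−f) + f·k]

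**Stoppers average, no effect left off cream (k = 1, ρ = 0).** Here R = (1−f)(1+g). For a constant effect with 3 of 25 off cream, R = 22/25 = 0.88.

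| True growth g | 1 of 25 off | 3 of 25 | 5 of 25 | 10 of 25 |
|---|---|---|---|---|
| 0% | 0.96 | 0.88 | 0.80 | 0.60 |
| 10% | 1.06 | 0.97 | 0.88 | 0.66 |
| 25% | 1.20 | 1.10 | 1.00 | 0.75 |
| 50% | 1.44 | 1.32 | 1.20 | 0.90 |

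Under these assumptions, any stopper shrinks a constant effect. A growing effect is understated, but it appears to fall (R < 1) only when f > g/(1+g).

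**Fewest subjects off cream, of 25, for a growing effect to appear to fall**

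| Assumption | Condition | g = 10% | g = 25% | g = 50% |
|---|---|---|---|---|
| k = 1, ρ = 0 | f > g/(1+g) | 3 | 6 | 9 |
| k = 2, ρ = 0 | f > g/(g+2) | 2 | 3 | 6 |
| k = 1, ρ = 0.5 | f > g/(g+0.5) | 5 | 9 | 13 |
| ρ = 1 | none | never | never | never |

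**How many might stop.** For assumed stop probabilities of 2%, 5%, 10% and 20%, the binomial chance of at least 1 stopper in 25 is 40%, 72%, 93% and over 99%. For at least 3 it is 1%, 13%, 46% and 90%.

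**What a split recovers.** In subjects who continue, with their own Week 4 value beside Week 8, the ratio is 1+g by construction, whatever f, k and ρ are.

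**Why the HPA split cannot simply be copied.** Protocol 7.9.2 defines suppression by any of three criteria: basal cortisol ≤5 µg/dL, 30-minute level ≤18 µg/dL, or rise <7 µg/dL. SAP 10.8.1 uses only a 30-minute level <18 µg/dL. A subject taken off cream for a low basal level or a small rise can therefore count as not suppressed in the SAP. Subjects who stop after clearing are not identified by HPA status at all.

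**One ambiguity in the count.** Protocol 5.4 refers Week 4 suppression to both 7.9.2 and 7.16 (Early Termination), while 7.9.2 keeps the subject in the trial to Week 8. These passages must be reconciled, because they decide how many off-cream subjects have Week 8 calcium.

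**The case against.** The case for leaving the plan alone has substance.

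- **Washout is assumed.** The reversibility statement in Protocol 7.13.6 covers elevated serum calcium after use above the recommended dose. It does not cover ordinary use, and it does not mention urinary calcium or the calcium:creatinine ratio, which are two of the three endpoints. A reader might infer that the protocol expects stoppers to show no change at Week 8; it does not say that.
- **The size may be small.** Protocol 2.2 describes HPA and calcium effects of marketed combinations as infrequent, and reports no significant calcium impact of topical calcipotriene at recommended amounts. With 1 or 2 of 25 off cream, dilution is 4% to 8% of an effect that may itself be near zero.
- **Stoppers need not absorb more.** A reader might infer that they do, since some were stopped for a steroid effect. HPA suppression reflects betamethasone and calcium reflects calcipotriene; nothing in the documents links the two, and subjects who stop after clearing are not selected on absorption. The k = 2 rows are illustration only.
- **Week 8 is not the sole calcium evidence.** Protocol 2.2 says this trial will be read together with serum calcium and calcium:creatinine data from the phase 3 trial.
- **Other displays help.** The shell prints medians and quartiles, on which a few stoppers have less influence, and by-subject listings would allow the split to be rebuilt by hand. The all-subject row is also a fair description of the assigned regimen with its stopping rules.
- **An on-cream row is selected after treatment began.** With f = 0.2 and k = 2, the whole arm at Week 4 averages 0.8×1 + 0.2×2 = 1.2, while continuers at Week 8 show 1.0 for a constant effect, which is 17% lower. Making that row the headline result would exchange one distortion for another.

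All of this stands as a limit on the size of the problem and on the remedy. None of it supplies the missing summary under continued use.

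**Conclusion.** The point holds as a reporting gap that is cheap to close. The Week 8 calcium rows combine subjects on and off cream, the plan separates them for HPA but not for calcium, and no planned summary isolates continued daily use, which is the condition named in the objective.

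If there is a calcium effect and it wanes off cream, the Week 8 mean is diluted by an amount that depends on an unknown stop rate. A constant effect would read as 0.96, 0.88 or 0.80 of Week 4 with 1, 3 or 5 of 25 off cream and nothing left of the effect. If the effect does not wane, or if there is none, the mixing creates no false decline.

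Two stronger readings are tempting and unsupported. One is that the Week 8 mean is certainly biased towards zero. The other is that a growing effect will look as though it fades. The first needs a washout that the protocol does not state for these endpoints under ordinary use. The second needs enough stoppers, for example 6 of 25 at 25% growth with average stoppers and full washout.

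**What to change.** In SAP 10.8.2.2 and Table 14.2.5:

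1. Keep the all-subject row.
2. Add Week 4 and Week 8 changes in the same subjects, by recorded cream use between the two visits: continued; stopped for HPA suppression; stopped or paused after clearing. Give n for each.
3. Classify from the dosing diary and the approved-stop records, not from the SAP's <18 µg/dL status. State in advance how missed doses and restarts are assigned.
4. Read the Week 4 to Week 8 course from the continued-use rows. Add a note that this group is selected after treatment began, may omit subjects with larger effects, and has a smaller n.
5. Make the population agree: HPA in the shell and list of tables, Safety in the text. Neither choice removes the mixing, because the HPA population excludes cream subjects only for lack of normal HPA function at baseline.
6. Reconcile Protocol 5.4 with 7.9.2 on whether subjects suppressed at Week 4 follow the early-termination procedures or continue to Week 8.

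The cost of the table change is a paragraph of SAP text and extra rows in one table. The data are already collected: SAP 10.4 uses approved-stop days for exposure, and Listings 16.2.5.1 and 16.2.5.4.1 carry stop dates and daily applications. Some groups may hold only a few subjects and should be read descriptively.

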#### **10.8.2.3 Adverse Events**

AE terms will be coded using MedDRA dictionary (version 20.0). A treatment-emergent AE (TEAE) is defined as an AE with a start date on or after the first application to trial medication (Day 1). If relationship to study medication is missing, the event will be conservatively summarized as being related to study drug. If intensity is missing, a separate category of missing intensity will be included in the summary table, and no imputation of severity will be performed. Through the data cleaning process, all attempts will be made to avoid missing values for relationship and severity.

All AEs will be presented in a by-subject listing, detailing the verbatim term given by the investigator, the PT, SOC, whether or not related to Cosyntropin or study procedure, location of AE to treatment area, start date, stop date, intensity, outcome, relationship to study medication (definitely, probably, possibly, and not related), action taken with study medication, action taken to treat the AE, seriousness and criteria for seriousness. For subjects assigned to MC2-01 cream, all TEAEs will be assigned to the Week 1-4 (starting from Day 1 to 28) or post-Week 4 period (starting from Day 29 and after) based on onset dates. Serious AEs and AEs leading to study drug discontinuation will be presented in a separate listing.

An overall summary of AEs will be presented by treatment and by period (MC2-01 group only). The summary will include the total number of events, frequency counts and percentages with:

- Any AE
- Any TEAE
- Any serious TEAE
- Any treatment-related TEAE
- Any TEAE leading to study drug discontinuation

Summaries of the incidence of TEAEs will be displayed by treatment and by period (MC2-01 group only) according to the following:

- All TEAEs by PT in descending order of frequency (the combined frequency of both treatments)
- All TEAEs by SOC, PT, and maximum severity (mild, moderate, or severe)
- All TEAEs by SOC, PT, and maximum relationship (recorded as 'definitely', 'probably', and 'possibly') to the study drug

At each level of summarization, a subject will be counted once if he/she reported one or more events. The severity of TEAEs and relationship to study drug will be summarized in a similar manner. For summaries of relationship to study drug, a subject will be classified according to the closest relationship. For summaries of TEAE severity, a subject will be classified according to the highest severity.

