### 6.3 Dosing Regimen

Subjects are to apply the trial product topically once daily, preferably in the evening, to affected areas on the scalp and the trunk (including the neck) and/or limbs, i.e., arms (including the back of the hands) and/or legs (including the buttocks and the top of the feet). The face, genitals, and intertriginous areas should not be treated with the investigational product. The first application is done under the supervision and instruction of the trial staff.

All subjects are instructed to apply the dose of trial medication in the morning on the day before the Week 2, Week 4 and for subjects assigned to the MC2-01 cream also at the Week 8 visit. On the day of the visit, the subjects should not apply any investigational product before the visit

Subjects are to record the date and time of application in the subject dosing diary. The weekly dose is not to exceed 100 g for the MC2-01 cream or for the comparator. The treated area should not exceed 30% of the BSA.

Detailed application instructions will be provided in the subject instructions.

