#### 7.10 Electrocardiogram

For all subjects assigned to the MC2-01 cream, a 12-lead ECG will be recorded at Visit 1/Day 0, Week 4 and Week 8 visits. Recording will take place after 5 minutes' rest in supine position.

Recordings will be promptly transmitted to the central ECG vendor for interpretation. Additional (unscheduled) ECGs can be recorded for safety reasons at any time based on the judgment of the investigator.

Clinically significant findings will be reported as medical history if detected at Visit 1/Day 0. At subsequent visits, any new clinically significant finding will be reported as an AE. Any ECG abnormalities will be carefully monitored and if necessary the subject will be withdrawn from the trial.

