#### **8.8.3 Adverse events**

Adverse events will be coded using Medical Dictionary for Regulatory Activities (MedDRA) terminology. Treatment-emergent adverse events will be summarized by the overall incidence of at least one event, incidence by body system, and incidence by body system and preferred term. Each subject will contribute only once (e.g., the first occurrence) to each of the rates, regardless of the number of occurrences (events) the subject experiences. Treatment-emergent AEs will be summarised by severity (mild, moderate, or severe), and by relationship to trial product (none, unlikely, possible, probable, or definite). An adverse event is treatment-emergent if its date of onset is Day 1 (Baseline) or later.

Discontinuations from the trial due to AEs and SAEs will be listed by subject.

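### The date-only TEAE rule counts cosyntropin reactions that occur before any cream as cream TEAEs beside ointment, and the SAP summaries do not separate them

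*SAP*

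**What the plan says.** **Procedures by arm.** Protocol 7.9.2 limits the challenge to one arm: "For subjects assigned to the MC2-01 cream, adrenal function will be assessed in a challenge test with an intravenous dose of adrenocorticotropic hormone". On timing it says "The ACTH challenge test will be performed at Visit 1/Day 0, Week 4 and Week 8 visits", and on order "The ACTH challenge test must be performed before application of the IP". Protocol 7.10 schedules 12-lead ECGs at the same three visits, again for cream subjects only. After Visit 1, "any new clinically significant finding will be reported as an AE"; a significant finding at Visit 1 itself goes to medical history. The comparator schedule (Table 7-3) has no row for either procedure.

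**Definition of treatment-emergent.** SAP 10.8.2.3: "A treatment-emergent AE (TEAE) is defined as an AE with a start date on or after the first application to trial medication (Day 1". Protocol 8.8.3: "An adverse event is treatment-emergent if its date of onset is Day 1 (Baseline) or later". SAP 9.2 sets Day 1 as the date of first application and equates it with Visit 1. The note under the Table 14.3.1.1 shell differs: it covers AEs that begin or get worse once the first dose has been given.

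**Attribution.** The by-subject AE listing shows "whether or not related to Cosyntropin or study procedure". No summary in SAP 10.8.2.3 or in Tables 14.3.1.1 to 14.3.1.4 uses that field.

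**Periods.** For cream subjects, SAP 10.8.2.3 assigns TEAEs to Weeks 1–4 up to study Day 28 and to the later period from Day 29. The footnotes under the Table 14.3.1.2 shell cut at the Week 4 visit instead and count the visit date in Weeks 1–4.

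**The concern.** Tables 14.3.1.1 to 14.3.1.4 set cream beside ointment for Weeks 1–4. The products contain the same active ingredients at the same strengths, so a difference in these columns will be read as a difference in formulation. One arm, however, receives an intravenous test agent that the other does not, and the first dose of it comes before any cream. Under the date rule an event caused by that injection is credited to the cream. Scheduled ECGs add a second imbalance, in detection: a finding without symptoms can surface at a scheduled ECG in the cream arm only.

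At stake is the reading of the any-TEAE, preferred-term, severity and serious-TEAE displays. The distortion runs against the cream. The sponsor evidently foresaw such events, because the field that would identify most of them is recorded, but it stops at the listing.

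**Working it through.** The plan states no figure on this point, so there is nothing to reproduce. The check traces the rules and then gives an illustration.

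**1. Scheduled procedures per subject**

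| | Cream (Table 7-2) | Ointment (Table 7-3) |
|---|---|---|
| Cosyntropin challenges | 3 | 0 |
| ECGs after Visit 1 | 2 | 0 |

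**2. Visit 1**

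- The challenge comes before the application (protocol 7.9.2). On the first application, protocol 6.3 says "The first application is done under the supervision and instruction of the trial staff".
- Both fall on one calendar date, which is SAP Day 1 (SAP 9.2).
- Protocol 7.13.1 and the AE listing record onset dates; neither mentions a clock time.
- A reaction between injection and first application therefore has a start date equal to Day 1, and it meets both the SAP 10.8.2.3 and the protocol 8.8.3 definitions.
- Under the Table 14.3.1.1 note it would not be a TEAE, but dates alone cannot apply that note to events on the same day.

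**3. Week 4**

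Protocol Day 0 is SAP Day 1, so SAP day = protocol day + 1. The visit window is protocol Day 28 ± 2.

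| Protocol day | SAP day | Period under SAP text | Period under table footnote |
|---|---|---|---|
| 26 | 27 | Weeks 1–4 | Weeks 1–4 |
| 27 | 28 | Weeks 1–4 | Weeks 1–4 |
| 28 | 29 | Post-Week 4 | Weeks 1–4 |
| 29 | 30 | Post-Week 4 | Weeks 1–4 |
| 30 | 31 | Post-Week 4 | Weeks 1–4 |

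Visit-day events from the Week 4 challenge or ECG are set beside ointment on 2 of the 5 window days under the text, and on all 5 under the footnote. Week 8 events fall in a column that has no ointment counterpart.

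**4. Size (assumed rates)**

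Inputs: about 60 subjects randomised 1:1 (protocol synopsis), so about 30 per arm. Assumed: a true TEAE rate of 20% in both arms; a probability r that a challenge produces an event; challenges independent of each other and of other events.

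Cream rate with k challenges in the period = 1 − 0.80 × (1 − r)^k.

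| r | k = 1 (Visit 1 only) | k = 2 (Week 4 included) | Ointment |
|---|---|---|---|
| 2% | 1 − 0.80 × 0.98 = 21.6% | 1 − 0.80 × 0.9604 = 23.2% | 20% |
| 5% | 1 − 0.80 × 0.95 = 24.0% | 1 − 0.80 × 0.9025 = 27.8% | 20% |
| 10% | 1 − 0.80 × 0.90 = 28.0% | 1 − 0.80 × 0.81 = 35.2% | 20% |

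In counts, each subject whose only TEAE comes from the challenge adds 1/30 = 3.3 percentage points. If 2%, 5% or 10% of 30 cream subjects have such an event, the expected numbers are 0.6, 1.5 and 3.0. The chance of at least one, 1 − (1 − r)^30, is 0.455, 0.785 and 0.958. With 25 subjects it is 0.397, 0.723 and 0.928. The ointment arm expects none from this source.

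**The case against.** The strongest reply has five parts.

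- **The SAP already excludes these events.** The Table 14.3.1.1 note would leave out a reaction before the first dose. That stands as evidence of two conflicting rules. It does not settle the matter, because the SAP text and the protocol both say otherwise and no recorded clock time would let the note be applied. A reader might infer that the SAP counts pre-application events without ambiguity; the note prevents so firm a statement.
- **Relatedness handles it.** Table 14.3.1.4 splits events by relationship to the study drug, and a cosyntropin reaction should be rated not related. This largely stands for the treatment-related rows, which are affected only if the event is judged related or the rating is missing and defaults to related. It does not help the any-TEAE, preferred-term or severity displays.
- **The listing suffices at this sample size.** A reader can go through flagged events for about 30 subjects per arm, but the table that gets quoted would not show them.
- **Little rests on it.** The planned between-arm inference is pharmacokinetic, and the AE tables carry no test or margin. This stands, and it limits the importance of the point.
- **ECG findings may be real.** A reader might infer that AEs found by scheduled ECG should also be removed. The documents do not support that. Protocol 2.3 names cardiac safety as a systemic concern and protocol 4.2 makes ECG change a safety endpoint for the cream. The AE listing has no field for how an event was detected, so removal would need judgement after the fact in an open-label trial and could hide a product effect.

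**Conclusion.** The point holds for the Visit 1 challenge under either period rule. By the SAP text and the protocol, a cosyntropin reaction before any cream is a cream TEAE in the columns beside ointment, and a table note contradicts this. For the Week 4 challenge it holds always under the table footnote, but under the SAP text only when the visit falls on protocol Day 26 or 27.

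With the assumed 20% background rate and 5% to 10% per challenge, the excess is 4 to 8 points from Visit 1 alone and 7.8 to 15.2 points if Week 4 counts in full. At 2% it is 1.6 and 3.2 points. None of these rates comes from the documents.

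Two stronger readings fail. The larger excess cannot be presented as the plan's consequence, because it requires the footnote's period rule. The post-Week 4 column is not a biased comparison between arms, because it has no ointment counterpart, although procedure events do raise the cream's rate there. No alpha or power is affected. This is a cheap improvement to descriptive safety tables and does not threaten the trial's main conclusions.

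**What to change.** 1. **Supplementary rows.** Keep every planned row in Tables 14.3.1.1 and 14.3.1.2. Add a row set for TEAEs excluding events recorded as related to cosyntropin or a study procedure, applied identically to both arms. Read it beside the all-TEAE row in any Weeks 1–4 statement on cream versus ointment, not in its place: the attribution is made open-label.
2. **One TEAE rule.** Reconcile SAP 10.8.2.3 with the Table 14.3.1.1 note. Day 1 events that can be identified as starting before the first application should not be treatment-emergent and should be listed separately. As only onset dates are recorded, flag these events at data review before database lock. State that they then leave the TEAE rows.
3. **One period rule.** Choose between the Day 28/29 cut and the Week 4 visit cut, and use it in the text and in all four table shells.
4. **ECG footnote.** Leave ECG-detected AEs in all rows and footnote that scheduled ECGs were done in the cream arm only.

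The cost is SAP wording, one extra display from a field already collected, and a short review step before lock. No new data collection is needed. Day 1 events whose timing cannot be established at review would stay in the TEAE rows; if they are recorded as cosyntropin- or procedure-related, the supplementary rows would still leave them out.
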